#### **6.11.4. Sensitivity Analyses**

A sensitivity analysis excluding patients who die within 48 hours of screening and have DNR or DNI in ITT analyses population will be conducted. The sensitivity analyses may include the following endpoints:

- time to recovery,
- proportion of patients who die or require non-invasive ventilation/high-flow oxygen or invasive mechanical ventilation (including ECMO) by Day 28, and
- all-cause mortality (Day 1 to Day 28).

#### **6.12. Bioanalytical and Pharmacokinetic/Pharmacodynamic Methods**

Plasma concentration data will be collected in patients who progress to intubation in ICU. The concentration-time data for baricitinib in these patients after NG tube administration will be primarily evaluated via graphical comparison to known pharmacokinetic (PK) profiles at 4-mg QD dosing that have been characterized for other populations such as healthy subjects, patients with rheumatoid arthritis, atopic dermatitis, etc. The observed individual data points and/or median and corresponding 90% CIs of plasma concentrations from patients with COVID-19 infection will be overlaid onto the estimated median and corresponding 90% prediction intervals of concentration-time profiles at 4-mg QD in the previous populations.

The PK data may also be analyzed using a population modeling approach via a nonlinear mixed-effects modeling (NONMEM) program, if the observed 4-mg exposure in the COVID-19 patients dramatically deviates from that in other patient populations and if adequate numbers of PK samples are available from patients who progress to intubation. The population PK model previously developed for baricitinib in aforementioned patient populations will be used for the modeling analysis. No PK/PD analyses will be conducted for this study.

#### **6.13. Safety Analyses**

The planned safety analyses are consistent with compound level safety standards, which are based on various sources, including company standards, internal and external subject matter experts, and cross-industry initiatives (for example, white papers produced by a Pharmaceutical Users Software Exchange [PhUSE] Computational Science Working Group [a collaboration with Food and Drug Administration (FDA) and PhUSE], published in the PhUSE Deliverables Catalog [PhUSE [WWW]]. Descriptions of the safety analyses are provided in this SAP; however, some details are in compound level safety standards.

A treatment-emergent adverse event (TEAE) during the analysis period is defined as an event that either first occurred or worsened in severity after the first dose of study treatment and on or prior to the end of the postbaseline period (defined as Day 28 for the primary outcome datalock).

A follow-up-emergent adverse event (FEAE) is defined as an event that either first occurred or worsened in severity after the treatment period and on or prior to the last visit date during the post-treatment follow-up period (up to the Day 60 visit) of the study.

**Table KHAA.6.8. Baseline and Postbaseline Definitions**

Analysis Type	Baseline	Postbaseline
1.1) Treatment-Emergent Adverse Events	The baseline period is defined as the start of screening and ends prior to the first dose of study treatment.	Starts after the first dose of study treatment and ends up to data cut date (for DMC interim analyses), or up to Day 28 for the primary outcome datalock.
1.2) Adverse Events including serious adverse events	NA	
1.3) Treatment-Emergent Abnormal Labs, Vital Signs and shift summaries in labs	Baseline will be all scheduled and unscheduled measurements recorded during the baseline period as defined above (1.1).	Postbaseline will be defined as above (1.1). All scheduled and unscheduled measurements will be included.
1.4) Change from Baseline for Labs, Vital Signs	The last scheduled nonmissing assessment recorded prior to the date of first dose of study treatment during the baseline period defined above (1.1).	Postbaseline will be defined as above (1.1). Only scheduled visits will be included. The early termination visits (ETV) are considered scheduled visits.

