## 5. Study Design

### 5.1. Summary of Study Design

Study I4V-MC-KHAA (KHAA) is Phase 3, multicenter, randomized, double-blind, placebo-controlled, parallel-group study designed to evaluate the efficacy and safety of baricitinib 4-mg given once daily (QD). The primary endpoint is the proportion of patients who die or require non-invasive ventilation/high-flow oxygen or invasive mechanical ventilation (including ECMO) by Day 28.

The study duration will be up to approximately 60 days over 3 study periods (see [Figure KHAA.5.1](#)):

- Screening: on Day 1 prior to dosing
- Treatment period: treatment is administered for up to 14 days, or up to the day of hospital discharge, whichever comes first, followed by treatment evaluations up to Day 28; and
- Follow-up: period starting after treatment evaluation, with a follow-up visit approximately 28 days after last dose of study drug and another follow-up visit at approximately Day 60.

Abbreviations: D = day; QD = once daily.

Note: Dosing occurs from the day of randomization until Day 14, or until hospital discharge, whichever comes first. Placebo or baricitinib are given with background therapy in keeping with local clinical practice for management of COVID-19, as defined in the protocol.

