### 6.1.2. Definition of Study Baseline

Unless otherwise specified, for efficacy and health outcomes, baseline is defined as the last nonmissing assessment recorded on or prior to, the first date that clinical status is assessed.

Baseline for safety analyses is described in [Table KHAA.6.8](#).

Change from baseline will be calculated as the visit value of interest minus the baseline value. If a baseline value or the value at the visit is missing for a variable, then the change from baseline is defined as missing.

The baseline of vital signs is defined as the vital signs collated at Day 1 from the case report form (CRF) Assessment for the National Early Warning Score (NEWS) (AVPU1001\_VS1001\_F1). The post baseline vital signs for analyses other than NEWS is defined as vital signs collated from CRF Vital Signs: Minimum and Maximum (VS1001).

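### SAP Table KHAA.6.8 row 1.4 cuts off the change-from-baseline baseline at the date of first dose, which excludes valid pre-dose Day 1 values taken on the dosing date and conflicts with rows 1.1 and 1.3 and with SAP 6.1.2

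*SAP*

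**What the plan says.** Table KHAA.6.8 (SAP 6.13) sets the safety baselines row by row.

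- **Row 1.1** (treatment-emergent adverse events): "The baseline period is defined as the start of screening and ends prior to the first dose of study treatment". The boundary is the dose itself.
- **Row 1.3** (treatment-emergent abnormal laboratory values and vital signs, and laboratory shifts): takes every measurement, scheduled or not, within the row 1.1 period.
- **Row 1.4** (change from baseline in laboratory values and vital signs): takes "The last scheduled nonmissing assessment recorded prior to the date of first dose of study treatment", and places that value within the row 1.1 period. The boundary is a calendar date, and the value must be a scheduled one.

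SAP 6.1.2 refers safety baselines to this table but also states its own vital-sign rule: "The baseline of vital signs is defined as the vital signs collated at Day 1 from the case report form (CRF", going on to name the form for the National Early Warning Score (NEWS). It adds: "If a baseline value or the value at the visit is missing for a variable, then the change from baseline is defined as missing".

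On timing, SAP 5.1 has "Screening: on Day 1 prior to dosing" and "Dosing occurs from the day of randomization until Day 14, or until hospital discharge, whichever comes first". SAP 5.3 randomizes at Day 1. The Schedule of Activities (Protocol 1.3) has no laboratory or vital-sign column before Day 1.

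**The concern.** Row 1.4 is stricter than the period it cites. A blood sample drawn in the morning and followed by a first dose in the afternoon lies inside the row 1.1 period but fails row 1.4, because its date is not earlier than the dosing date. No earlier scheduled visit exists to fall back on. The same patient can therefore have a baseline for the shift tables and none for change from baseline.

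Two outputs are at stake. One is the change-from-baseline version of the box plots in SAP Tables KHAA.6.10 and KHAA.6.11. The other is the ANCOVA of continuous safety variables, with baseline value in the model, in Protocol 9.4.1 and 9.4.4. Patients without a baseline cannot contribute to either. Those who remain would be the ones whose Day 1 work happened to fall on an earlier date than their first dose.

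Where an earlier-dated scheduled value does exist, row 1.4 prefers it to a later pre-dose value from the dosing date, so the baseline is older than it need be.

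**Working it through.** The plan states no figure on this point, so the check applies the two rules to the sampling patterns that the schedule allows.

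**Inputs**
- Screening on Day 1 before dosing, and dosing from the day of randomization: SAP 5.1. Randomization at Day 1: SAP 5.3.
- Day 1 tolerance of up to 3 days; laboratory timing of plus or minus 1 day; eligibility look-back of 24 hours for most tests and 2 days for LDH, CRP, ferritin and D-dimer: Protocol 1.3.
- Date and time of every dose are recorded: Protocol 6.4.

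**Rules**
- Date rule (row 1.4): usable if sample date < date of first dose.
- Dose rule (rows 1.1 and 1.3): usable if sample time < time of first dose.

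**Applied to a first dose at 14:00**

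| Sample | Row 1.4 | Rows 1.1 and 1.3 |
|---|---|---|
| Same date, 09:00 (5 h before) | excluded | kept |
| Previous date, 18:00 (20 h before) | kept | kept |
| Two dates earlier, 18:00 (44 h before) | kept | kept |
| Same date, 16:00 (2 h after) | excluded | excluded |

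The rules differ only in the first line, the valid pre-dose sample on the dosing date. That line is also the nominal schedule. The table assumes that an earlier-dated sample counts as scheduled.

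**Consequence for that patient.** Day 1 is the first scheduled assessment, so if all Day 1 samples fall on the dosing date, no value passes row 1.4. SAP 6.1.2 then sets change from baseline to missing.

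**Vital signs.** Protocol 8.2.1 bases NEWS on the latest readings before study drug is given, and SAP 6.1.2 makes the Day 1 NEWS-form values the baseline. Row 1.4 rejects those readings when they share the dosing date. The SAP thus gives two baselines that cannot both apply.

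**Size.** The share of patients sampled only on the dosing date is not stated. The bounds are 0% (all have a scheduled value on an earlier date) and 100% (all sampled only on the dosing date). As an illustration only, assume one pre-dose sample per patient, uniform over the 24 hours before a dose given at clock hour h, with earlier-dated samples counted as scheduled. The excluded share is h/24:
- h = 6: 6/24 = 25%, or 0.25 × 1400 = 350 patients
- h = 12: 12/24 = 50%, or 0.50 × 1400 = 700 patients
- h = 18: 18/24 = 75%, or 0.75 × 1400 = 1050 patients

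If an accepted pre-entry test does not count as scheduled, samples of that kind fail row 1.4 as well, and the share rises.

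**After correction.** With the dose rule in row 1.4, the first line of the table changes to kept and the other three are unchanged.

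**The case against.** The strongest reply is that this is loose drafting with a narrow effect. Row 1.4 ties itself to the row 1.1 period, so the author may have meant the dose and written the date. SAP 6.13 leaves some details to compound-level safety standards, which are not available here. The protocol also lets Day 1 procedures spread over several dates and lets laboratory samples be taken a day early, so some patients will have an earlier-dated value.

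The point about spread stands, and it means the loss is conditional. It does not remove the defect. The look-back is, for most tests, an eligibility provision, and the documents do not say that such a test is stored as the scheduled Day 1 record, which row 1.4 requires. Vital signs have no look-back; only the general Day 1 tolerance could put them on an earlier date. A programmer who silently used the dose instead of the date would depart from the written SAP.

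Three stronger readings are tempting, and the documents support none of them.

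- *That the Day 1 baseline is always lost.* It is lost only when taken on the dosing date. For vital signs the SAP contradicts itself rather than plainly discarding Day 1.
- *That monitoring of the hepatic, haematologic, renal and creatine phosphokinase topics in SAP 6.13.5 is compromised.* That section identifies topics through MedDRA queries, term lists or treatment-emergent laboratory changes. The last of these fall under row 1.3, which keeps same-date pre-dose values.
- *That a known, large number of the 1400 patients drop out, or that the arms are biased against each other.* Any count rests on an assumed share. The trial is double-blind, and nothing in the documents links sampling date to treatment. The demonstrated cost is fewer patients and a group selected by sampling date.

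It is also fair to note that the SAP tables list box plots but no ANCOVA. The ANCOVA consequence rests on the protocol text.

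**Conclusion.** Row 1.4 is wrong as written, and the effect is limited to safety change-from-baseline outputs. It excludes valid pre-dose values taken on the dosing date, disagrees with rows 1.1 and 1.3, and for vital signs disagrees with SAP 6.1.2. A patient whose scheduled Day 1 values all fall on the dosing date has no change from baseline. The affected share is unknown, between 0% and 100%.

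The conclusion assumes a literal reading of the row and that no unseen standard overrides it. Treatment-emergent and shift analyses, the safety topics identified through them, efficacy, alpha allocation and sample size do not depend on it. It should be corrected because the remedy is cheap and the SAP already handles the same issue properly elsewhere: SAP 6.8.3 uses both date and time to classify events on the day of first dose.

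**What to change.** In SAP Table KHAA.6.8 row 1.4:

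1. Replace the cut-off at the date of first dose with a cut-off at the first dose, by date and time.
2. If the sample time is missing, accept a scheduled Day 1 value only when it is dated on or before the date of first dose. The date limit is needed because laboratory samples may be taken up to 1 day late, so a value labelled Day 1 can be dated after dosing began.
3. State that an accepted pre-entry local test used as the Day 1 value counts as scheduled.
4. Keep one vital-sign baseline by aligning row 1.4 with SAP 6.1.2, with the same wording in both places.

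The cost is a few sentences in the SAP and one programming condition; dose times are already collected. The downside is that some untimed samples from the dosing date may in fact be post-dose. The protocol states no rule for recording the time of local laboratory samples, so the number of untimed values admitted should be reported with the outputs.

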# **1.3.** Schedule of Activities (SoA)

Day 1 procedures may be conducted over more than 1 day, as long as all activities are completed within the allowed interval tolerance. Activities at the first follow-up visit (28 days after last dose) are required for all randomized patients and can be conducted as a telephone visit. Activities at the second follow-up visit (on Study Day 60) are also required for all randomized patients and can be conducted as a telephone visit. If a telephone visit is conducted after hospital discharge, assessments will include: concomitant medications, adverse events, COVID-19 clinical symptoms, and Clinical Status Assessment. Collection of laboratory samples is preferred at designated timepoints, but it will not be a protocol deviation if, after hospital discharge, phone visits are conducted and laboratory samples are not collected because the visits are by telephone. See the Comments column for details about daily collection of clinical assessments and vital signs.

Study day	1	4	7	10	14	28	Follow-up (28 Days after Last Dose)	Follow-up Day 60	ETV	Unsched uled	Comments
Interval tolerance (days)	≤3		_	_	_	_	±4	+7	_	—	If patient is discharged from hospital, the study visit may include a visit interval tolerance (window) of $\pm 2$ at Study Day 4, Day 7, Day 10, Day 14, and Day 28.
Site Visit		X	X	x	x	x					Site visit is preferred after discharge, but telephone visit is acceptable after discharge and should include collection of concomitant medications, adverse events, COVID-19 clinical symptoms, and Clinical Status Assessment. Failure to conduct activities that cannot be reasonably performed over the telephone will not be considered a protocol deviation.
Telephone Visit							X	Х			
Informed consent	Х										
Inclusion and exclusion criteria	Х										
Demographics	Х										
Pre-existing conditions and medical history, including relevant surgical history	X										Obtained from interview or available information, for example, medical records.

Study day	1	4	7	10	14	28	Follow-up (28 Days after Last Dose)	Follow-up Day 60	ETV	Unsched uled	Comments
Interval tolerance (days)	≤3	_	_	_	_	_	±4	+7	_	_	If patient is discharged from hospital, the study visit may include a visit interval tolerance (window) of $\pm 2$ at Study Day 4, Day 7, Day 10, Day 14, and Day 28.

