**Table KHAA.6.1. General Methods for Statistical Analysis**

Data Type	Purpose	Analysis
Categorical/discrete data	Summary and descriptive analysis	Number of patients with available data (n), either observed or imputed, at the relevant time point, and will be presented as frequency counts and percentages. Percentages will be calculated using the total number of patients in the analysis population included as the denominator. Percentages will generally be presented to 1 decimal place but will not be presented for zero counts.
	Treatment comparison	Logistic regression analysis
Continuous data	Summary and descriptive analysis	Number of observations, mean, standard deviation (SD), standard error of the mean (SEM), median, 1st quartile, 3rd quartile, minimum, and maximum. The minimum and maximum will be reported to the same number of decimal places as the raw data recorded in the database. The mean, first quartile, median, and third quartile will be reported to 1 more decimal place than the raw data recorded in the database. The SD and SEM may be reported to 2 more decimal places than the raw data recorded in the database. Any exceptions will be noted in the programming specifications. P-values for primary and key secondary analyses will be reported to as many decimal places as needed ( $\geq 5$ ).
	Treatment comparison	Analysis of variance (ANOVA), mixed model repeated measures (MMRM), Wilcoxon rank-sum test
Ordinal data	Treatment comparison	Proportional Odds model, Wilcoxon rank-sum test
Time to event data	Treatment comparison	Log-rank test, Kaplan-Meier curves, Cox proportional hazards. As needed: Fine-Gray model, Max-combo test

Note: the detail of the analysis method defined in Section 6.2.

Change from baseline will be calculated as the visit value of interest minus the baseline value. If the baseline value is missing for a particular variable, then it will not be imputed and the change from baseline and percent change (or percent improvement) from baseline will not be calculated.

For all models, patients will be excluded who do not have the necessary covariates to run the model.

For the primary and key secondary analyses that rely on OS values, the patient's worst ordinal score for the day will be used.

The Per Protocol Set (PPS) will be used if needed for post hoc analyses.

Throughout this document, "Day x" refers to Study Day x.

Additional supportive analyses will be performed as needed.

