**Table KHAA.6.2. Definition of Study Period Time Intervals**

Study Period	Interval Start Definition	Interval End Definition
Screening: All participants who sign informed consent are considered as entering the Screening Period.	Informed consent date	Prior to the start of Treatment Period.
Post-Treatment Follow-Up: All participants who had a follow up visit are considered as entering follow-up period.	After the Treatment Period ends.	The maximum of the last study visit date or study disposition date.

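### The lab change-from-baseline rule stops at the date of first dose, so it discards a pre-dose sample drawn on the dosing day and leaves no eligible date when consent and first dose fall on one day

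*SAP*

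**What the plan says.** SAP 6.1.2 sends safety baselines to Table KHAA.6.8. Row 1.4, which covers change from baseline for labs and vital signs, takes "The last scheduled nonmissing assessment recorded prior to the date of first dose of study treatment during the baseline period defined above (1.1"). Row 1.1, the period it cites, reads "The baseline period is defined as the start of screening and ends prior to the first dose of study treatment". Row 1.3, for treatment-emergent abnormalities and shifts, uses every measurement in the row 1.1 period.

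The start of that period comes from SAP Table KHAA.6.2, which opens screening on the informed consent date: "All participants who sign informed consent are considered as entering the Screening Period".

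On timing, SAP 5.1 gives "Screening: on Day 1 prior to dosing" and "Dosing occurs from the day of randomization until Day 14, or until hospital discharge, whichever comes first". Protocol 1.3 adds "Day 1 procedures may be conducted over more than 1 day, as long as all activities are completed within the allowed interval tolerance", with a Day 1 tolerance of up to 3 days.

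On missing baselines, SAP 6.1.2 states "If a baseline value or the value at the visit is missing for a variable, then the change from baseline is defined as missing", and SAP 6.1 states "For all models, patients will be excluded who do not have the necessary covariates to run the model".

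**The concern.** Row 1.4 is stricter than the period it refers to. A lab drawn before the first dose on the dosing day is baseline for the shift tables but not for change from baseline, and the SAP gives no reason for the difference.

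The stricter rule also conflicts with the design. Consent, screening labs, randomization and first dose on one date is the schedule as planned. A patient who follows it has no date that satisfies row 1.4.

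At stake are the change-from-baseline lab results. Protocol 9.4.1 and 9.4.4 plan an ANCOVA with the baseline value in the model for continuous safety measures, laboratory variables included, and 9.4.4 also plans mean change by visit. An affected patient would drop out of all of these. If the programmers instead used the same-day sample, the analysis would depart from the written SAP.

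**Working it through.** The plan gives no figure to reproduce. The check is a count of the dates each rule admits.

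**Inputs**
- Baseline period starts on the consent date (SAP Table KHAA.6.2). Call it date 0.
- First dose is on date D.
- D runs from 0 to 3. This range is an assumption, taken from the Day 1 tolerance in protocol 1.3.
- Row 1.4 condition: consent date ≤ lab date < dose date.
- Rows 1.1 and 1.3 condition: consent date ≤ lab date, and lab drawn before the dose.

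**Count**
- Row 1.4 admits dates 0 to D − 1, which is D dates.
- A window ending at the dose admits dates 0 to D, with date D pre-dose only, which is D + 1 dates.
- The difference is (D + 1) − D = 1, and the date lost is always the dosing date.

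| Days from consent to first dose (D) | Dates admitted by row 1.4 | Dates admitted if the window ends at the dose |
|---|---|---|
| 0 | 0 | 1 |
| 1 | 1 | 2 |
| 2 | 2 | 3 |
| 3 | 3 | 4 |

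**Scheduled samples.** The Schedule of Activities has no visit before Day 1, and the next lab visit is Day 4. So there is 1 scheduled pre-dose lab set, and row 1.4 accepts scheduled assessments only. If that set is drawn pre-dose on date D, 0 of 1 remain, whatever D is.

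**Could another provision supply the baseline?**
- *Earlier hospital labs.* Tests from the 24 hours before study entry (2 days for LDH, CRP, ferritin and D-dimer) are accepted for eligibility. If drawn before the consent date, they precede the row 1.1 period and do not count.
- *The reading of 'prior to' in SAP 6.1.3.* It is tied to Table KHAA.6.2. Applied here, it would still not admit the dosing date.
- *The Day 1 baseline in SAP 6.1.2.* It covers vital signs only.

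**Does the plan use clock time elsewhere?** Yes. SAP 6.8.3 uses both date and time to classify events on the first-dose day, and protocol 6.4 has the date and time of each dose recorded.

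**The case against.** The strongest reply is that little depends on this row. SAP Table KHAA.6.10 lists no ANCOVA for labs. Its only change-from-baseline lab output is a set of box plots that may show observed values, changes, or both. The model exclusions therefore rest on protocol text that the SAP's lab table does not repeat. This stands, and it limits the importance of the point.

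Lab timing is also flexible: the Schedule of Activities allows one day either side of the designated day. A Day 1 sample drawn the day before dosing, after consent, is kept. That reduces the number affected but does nothing for a sample drawn on the dosing date.

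A date-only cut-off has one merit: it guarantees a pre-dose value without clock times. The documents require times for doses and pharmacokinetic samples, but no such requirement was found for local safety labs, so the share of untimed samples is unknown. Treating these as pre-dose is nevertheless reasonable. Neutrophils, lymphocytes, ALT/AST and eGFR decide eligibility (protocol 5.2, criteria 17 to 20), so they are normally drawn before randomization and dosing.

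Pre-consent hospital labs would remain outside the baseline period even after the change. That is true, but it is a separate gap that affects row 1.3 as well.

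Finally, SAP 6.13 says some details sit in compound level safety standards, which were not available for this review. They may contain a working rule for same-day labs, but nothing in the SAP says they override an explicit definition in its own table.

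**Conclusion.** The concern holds on the text. Row 1.4 always excludes the dosing date, and it admits no date at all when consent and first dose coincide. A patient whose only scheduled pre-dose set was drawn on the dosing date has no lab baseline, so change from baseline is missing.

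The number of patients affected cannot be computed, because the documents give no consent, sampling or dosing dates. Since Day 1 procedures may span up to 3 days, some Day 1 samples will precede the dosing date and be kept.

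The consequence is small. It reaches change-from-baseline lab summaries and any model that needs the lab baseline. Observed-value plots, shift and treatment-emergent tables, and efficacy are unaffected. The loss should be similar in the two arms, because the rule does not depend on treatment. This is an inexpensive improvement and does not threaten the trial's conclusions.

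**What to change.** In row 1.4, for labs, end the window at the first dose instead of at the date of first dose, judged by date and time. If a scheduled Day 1 sample drawn on the dosing date has no recorded time, treat it as pre-dose. Leave the start of the baseline period, rows 1.1 and 1.3, and the vital-sign baseline as they are. Because row 1.4 covers labs and vital signs together, the lab rule needs its own line.

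The cost is a short text change and a revised date filter, with no new samples. The downside is that some untimed Day 1 samples may in fact be post-dose. Reporting how many baselines rest on that default would show whether it matters.
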